### 5.2.2 Subject Disposition

Subject disposition will be summarized by treatment group for FAS and the Safety Analysis Set. The number (percentage) of subjects who completed or discontinued prematurely from the study and their reason for discontinuation will be summarized by treatment group. In addition, the number of subjects screened and the number and percentage of subjects who failed screening and the reasons for screen failure will be summarized, based on data recorded on the Screening Disposition CRF.

### 5.2.3 Protocol Deviations

Major protocol deviations will be identified, reviewed and documented by the clinical team prior to database lock/treatment unblinding. All protocol deviations will be categorized according to standard classifications including the following:

- Violations of inclusion/exclusion criteria
- Noncompliance with protocol procedures/assessments
- Noncompliance of drug dosage
- Use of prohibited treatments

All significant protocol deviations will be listed, and summarized by category and by treatment group.

### 5.2.4 Demographic and Other Baseline Characteristics

Demographic and other baseline characteristics for the FAS and Safety Analysis set will be summarized for each treatment group and overall using descriptive statistics or frequency count. Continuous demographic variables include age, weight, height and body mass index (BMI); categorical variables include age group (<65, and  $\geq 65$  years old), sex, ethnicity, race, region and country. The following baseline disease characteristics will also be summarized:

- Baseline platelet count and its category ( $<40 \times 10^9/L$  and  $40$  to  $<50 \times 10^9/L$ )
- Bleeding risk associated with the elective procedure (low, moderate and high based on Amendment 02 categorization) and the type of elective procedure
- HCC status (yes and no) and Barcelona-Clinic Liver Cancer (BCLC) stage (0, A, B, C and D)
- Model for End-stage Liver Disease (MELD) score
- Child-Turcotte-Pugh (CTP) score and CTP grade (A, B and C)
- Baseline international normalized ratio (INR) and its category ( $\leq 1.6$  and  $>1.6$ )
- Portal vein flow rate as per Doppler Sonography assessment
- Creatinine clearance and disease etiology.

### MEDICAL HISTORY

All medical histories as documented by the Investigator will be coded using the Medical Dictionary for Regulatory Activities (MedDRA).

The number (percentage) of subjects reporting a history of any medical condition will be summarized by System Organ Class (SOC), preferred term for each treatment group and overall based on FAS.

### 5.2.5 Prior and Concomitant Therapy

All investigator terms for medications recorded on the CRF will be coded using the WHO Drug Dictionary (WHO DD).

Prior medications are defined as medications that stop prior to the first dose of study drug. Concomitant medications are defined as medications that (1) start before the first dose of study drug and are continuing at the time of the first dose of study drug, or (2) start on or after the date of the first dose of study drug, up to 30 days after the last dose of study drug.

The number (percentage) of subjects who take prior and concomitant medications will be summarized using the Safety Analysis Set by treatment group, Anatomical Therapeutic Chemical (ATC) Classification, and WHO DD preferred term. In addition, the number (percentage) of subjects who take the concomitant medications associated with elective procedures will also be summarized using the Safety Analysis Set by treatment group, ATC Classification, and WHO DD preferred term.

If a subject takes the same medications for the same class level or drug name, the subject will be counted only once for that class level or drug name.

### 5.2.6 Treatment Compliance

Treatment compliance is defined as follows:

$$\frac{\text{Total number of tablets dispensed} - \text{total number of tablets returned}}{\text{Total number of tablets subject should have taken}}$$

Treatment compliance will be summarized using descriptive statistics by treatment group based on FAS and Safety Analysis Set. Treatment compliance will also be summarized by treatment group using the categories <80%, ≥80% to ≤100%, >100% to ≤120%, and >120%.

## 5.3 DATA ANALYSIS GENERAL CONSIDERATIONS

The FAS will be used as the primary population for all efficacy analyses, while the PP will be used in supportive analyses of the primary efficacy endpoint and Safety analysis set will be used for all safety analyses. Unless stated otherwise, all efficacy analyses will be performed at  $\alpha=0.05$  significance level and only descriptive statistics or frequency count will be generated for safety analyses without any hypothesis testing.

### 5.3.1 Pooling of Centers

This study is a multicenter international study with an estimated 100 centers participating in the study. Due to small expected number of subjects in each center, all analyses will be performed with all centers pooled across the study unless stated otherwise. Consistency of results across geographic regions will be examined as specified in the respective sections in this document.

### 5.3.2 Adjustments for Covariates

The primary efficacy endpoint, the proportion of subjects without platelet transfusion or any rescue procedure for bleeding, and the first secondary efficacy endpoint, proportion of subjects with platelet count  $\geq 50 \times 10^9/L$  on Procedure Day, will be analysed separately within each

baseline platelet count cohort ( $<40 \times 10^9/L$  or from 40 to  $<50 \times 10^9/L$ ) using the Cochran-Mantel-Haenszel (CMH) test adjusting for the risk of bleeding associated with the elective procedure (low, moderate, or high based on Amendment 02 categorization). Since the HCC status is included in the randomization stratification for safety purposes only, not for efficacy consideration, HCC will not be included in the CMH model for the primary efficacy analysis.

### 5.3.3 Multiple Comparisons/Multiplicity

The primary efficacy endpoint will be tested between the individual avatrombopag treatment group (40 or 60 mg) and matching placebo within each baseline platelet count cohort ( $<40 \times 10^9/L$  or from 40 to  $<50 \times 10^9/L$ ), each at a significance level of  $\alpha=0.05$ . The primary efficacy endpoint is considered positive only if the tests are statistically significant for both baseline platelet count cohorts to control the family-wise Type I error rate at a significance level of  $\alpha=0.05$ .

A sequential gatekeeping testing procedure will be used for the secondary efficacy endpoints to control the family-wise Type I error rate at a significance level of  $\alpha=0.05$ . The secondary efficacy endpoints will be analyzed if the primary efficacy endpoint is statistically significant for both baseline platelet count cohorts. The first secondary efficacy endpoint is tested first within each baseline platelet count cohort, each at a significance level of  $\alpha=0.05$ . Only if the first secondary efficacy endpoint is statistically significant for both baseline platelet count cohorts, the analysis of second secondary efficacy endpoint will proceed within each baseline platelet count cohort, each at a significance level of  $\alpha=0.05$ . No alpha adjustment is planned for other efficacy endpoints.

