The 95% confidence interval (CI) for the proportion of subjects not requiring a platelet transfusion or any rescue procedure for bleeding will be calculated for each treatment group within each baseline platelet count cohort. In addition, the 95% CI for the difference between avatrombopag and matching placebo will be provided within each baseline platelet count cohort.

Since the HCC status is included in the randomization stratification for safety purposes only, not for efficacy consideration, HCC will not be included in the CMH model for the primary efficacy analysis.

Subjects with missing information about the primary efficacy outcome due to early withdrawal or other reasons will be considered as having received a transfusion for the primary analysis.

The following analyses will be considered as sensitivity analyses:

- PP analysis: The same primary efficacy analyses described above will be repeated based on the PP analysis set.
- Observed case: The same primary efficacy analyses described above will be repeated based on observed data. Subjects with missing information about the primary efficacy outcome will be excluded from this analysis.
- Fisher's exact Test: The same primary efficacy analyses described above will be carried out using Fisher's exact test.
- Modified primary efficacy endpoint: Proportion of subjects who do not require a platelet transfusion after randomization and up to 7 days following an elective procedure. This efficacy endpoint will be analyzed using the same approach as primary efficacy analysis using FAS.

Additional sensitivity analyses may also be explored, if deemed appropriate.

SECONDARY EFFICACY ANALYSES

There are 2 secondary efficacy endpoints in this study: (revised per Amendment 04)

- Proportion of responders defined as subjects who achieve target platelet counts of $\geq 50 \times 10^9/L$ on Procedure Day (prior to receiving a platelet transfusion or undergoing the elective procedure)
- Change from baseline in platelet count on Procedure Day (prior to receiving a platelet transfusion or undergoing the elective procedure)

The analysis of the secondary efficacy variables as defined above will proceed following a sequential gatekeeping testing procedure with the multiplicity adjustment to control the Type I error rate at significance level $\alpha=0.05$.

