#### 5.4.2 Secondary Efficacy Analyses

There are 2 secondary efficacy endpoints in this study:

- Proportion of responders, defined as subjects who achieve target platelet counts of  $\geq 50 \times 10^9/L$  on Procedure Day (prior to receiving a platelet transfusion or undergoing the elective procedure)
- Change from baseline in platelet count on Procedure Day (prior to receiving a platelet transfusion or undergoing the elective procedure)

The analysis of the secondary efficacy variables, as defined above, will proceed following a sequential gatekeeping testing procedure to control the family-wise Type I error rate at a significance level of  $\alpha=0.05$ .

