##### 5.4.2.2 Change from baseline in platelet count on the Procedure Day

The second secondary efficacy variable, change from baseline in platelet count on the Procedure Day, will be analyzed only if the first secondary efficacy variable is statistically significant for both baseline platelet count cohorts.

The change from baseline in platelet count on Procedure Day will be analyzed using the Wilcoxon rank sum test separately within each baseline platelet count cohort ( $< 40 \times 10^9/L$  or from 40 to  $< 50 \times 10^9/L$ ), each at a significance level of  $\alpha=0.05$ . The treatment difference

between avatrombopag and placebo will be provided within each baseline platelet count cohort using Hodges-Lehmann estimation along with associated asymptotic (Moses) 95% CIs.

Last observation carried forward will be used for subjects with missing platelet count on Procedure Day for this analysis.

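### Does the plan lose Type I error control on the secondary endpoints because it never says that both platelet cohorts must be significant?

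*SAP*

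**What the plan says.** SAP 5.3.3 tests the primary and both secondary endpoints separately in the two cohorts (below 40, and 40 to below 50 × 10⁹/L), each test at 0.05.

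- **Primary.** "The primary efficacy endpoint is considered positive only if the tests are statistically significant for both baseline platelet count cohorts". Family-wise control at 0.05 is given as the reason.
- **Secondaries, purpose.** "A sequential gatekeeping testing procedure will be used for the secondary efficacy endpoints to control the family-wise Type I error rate", again at 0.05.
- **Gate from primary to secondaries.** "The secondary efficacy endpoints will be analyzed if the primary efficacy endpoint is statistically significant for both baseline platelet count cohorts".
- **Gate from first to second secondary.** The sequence moves on under this condition: "Only if the first secondary efficacy endpoint is statistically significant for both baseline platelet count cohorts". The sentence then closes with "the analysis of second secondary efficacy endpoint will proceed within each baseline platelet count cohort, each at a significance level of" 0.05.

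SAP 5.4.2 repeats that the secondary analysis "will proceed following a sequential gatekeeping testing procedure to control the family-wise Type I error rate at a significance level of" 0.05. SAP 5.4.2.2 says that change from baseline "will be analyzed using the Wilcoxon rank sum test separately within each baseline platelet count cohort". Protocol 9.7.1.6 makes the same promise, "a sequential gatekeeping testing procedure with the multiplicity adjustment to control the Type I error rate at significance level" 0.05, with the same gate between the two secondaries, and the synopsis repeats it. None of these places says when a secondary endpoint is declared significant.

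The secondary efficacy objectives (SAP 3.1.2, Protocol 8.2) are each written as one superiority claim, not one per cohort or per dose.

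**The concern.** A gate says when the next test may be run. A success rule says what may be claimed. SAP 5.3.3 writes a success rule for the primary and only gates for the secondaries. For the first secondary, the both-cohorts condition at least appears as the gate to the next test. The second secondary is last in line, so no later gate shows what counts as success. Its tests are set cohort by cohort at 0.05, and the text stops there.

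If someone took this to mean that each cohort's result could be claimed separately, there would be two independent chances of a false claim at 0.05 each, with no adjustment. The 0.05 control stated in SAP 5.3.3, SAP 5.4.2 and Protocol 9.7.1.6 would then not hold for two-sided errors. It would also be unclear before unblinding what a secondary result significant in one cohort only means.

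**Working it through.** **Inputs**

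- Two cohorts of different subjects, so the cohort tests are independent (SAP 3.2).
- Level 0.05 per cohort for each endpoint; stated family-wise level 0.05 (SAP 5.3.3).
- 67 avatrombopag and 33 placebo subjects per cohort; primary response 18% on placebo and a 35-point difference, so 18% + 35% = 53% on avatrombopag; Fisher's exact test, two-sided 0.05 (SAP 4).
- Phase 2 responder rates 48.4% and 8.1% (Protocol 7.1.2.3). These are a proxy only, because that endpoint also required a rise of at least 20 × 10⁹/L and was read on Days 4 to 8.
- The documents give no effect size for either secondary.

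**1. The plan's own figures.** Exact Fisher power at 53% against 18% with 67 and 33 subjects is 0.926, which agrees with the stated power above 90% per cohort.

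For the 0.05 family-wise level, require both cohorts for each secondary:

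- endpoint null in both cohorts: 0.05 × 0.05 = 0.0025;
- endpoint null in one cohort, with the other certain to reject: 1 × 0.05 = 0.05.

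Testing in fixed order with both-cohorts gates keeps the sequence at or below 0.05. A simulation of the gated sequence (1,000,000 runs per scenario, primary taken as passed, correlation between the secondaries 0 or 0.7) gave 0.0025 and about 0.05 in the matching scenarios. The stated figure is reproduced.

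**2. The rival reading.** If one-cohort claims were allowed:

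- two-sided: 1 − 0.95² = 0.0975;
- counting only false claims in favour of avatrombopag: 1 − 0.975² = 0.0494.

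For the second secondary, 0.0975 needs three things together: a one-cohort claim, the endpoint null in both cohorts, and the first secondary already passed in both. Both secondaries use the same pre-transfusion Procedure Day count (SAP 5.1.2). A real difference in reaching 50 × 10⁹/L with no difference in change from baseline is barely coherent within a randomised cohort. It is not strictly impossible, because the missing-data rules differ: non-response for the first (SAP 5.4.2.1), last observation carried forward for the second (SAP 5.4.2.2).

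This was checked by simulating both endpoints from one count. Assumptions: 67 against 33 per cohort; baselines uniform on 20–40 and 40–50; normal change with SD 10, 15 or 20; primary gate taken as passed; an unstratified Mantel-Haenszel test and a Wilcoxon test. With no platelet effect, the first secondary passed in both cohorts in 0.17% to 0.27% of trials. A false second-secondary result in at least one cohort followed in 0.06% to 0.17%. With no platelet effect, the gate therefore does most of the protecting, even under the looser reading.

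**3. How often would the reading matter?** This is the chance that exactly one cohort is significant.

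- First secondary at the Phase 2 proxy rates: power 0.9943, so 2 × 0.9943 × 0.0057 = 0.011.
- First secondary if it had the primary's assumed rates: 2 × 0.926 × 0.074 = 0.137.
- Second secondary, after the first passed in both cohorts (same simulation model, with effect): at most 0.0246 in any setting tried, and at most 0.0015 where the first secondary has power of at least 0.84 in each cohort.

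The two first-secondary figures ignore the primary gate, use Fisher's test rather than the planned CMH, and apply the same rates to both cohorts although the higher one starts next to the threshold. They show a range and do not predict a frequency.

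**4. Which reading does the text support?**

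- The phrase setting each test at 0.05 within each cohort is also used for the primary, immediately before its both-cohorts rule. It describes the tests and does not license separate claims.
- Significance in both cohorts is the only status the plan defines for the first secondary (SAP 5.3.3, SAP 5.4.2.2, Protocol 9.7.1.6).
- Each objective is one claim.
- The stated two-sided 0.05 control is guaranteed only if both cohorts are required.
- No section permits a claim from one cohort.

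**The case for a change.** The best case for a change is that the plan itself separates gates from success rules, because it wrote both for the primary, so the omission for the secondaries cannot be put down to style. Each cohort also has its own dose, so a one-cohort claim is one that somebody might want to make. Treating the gate as a success rule settles only the first secondary. If the second is still claimed by cohort and the first is real, the simulated error stays at 0.097 to 0.098.

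Part of this stands. The success sentence is missing, most visibly for the second secondary, and writing it would cost nothing. The favourable-direction figure of 4.94% does not dispose of the point either, since the usual one-sided standard would be 2.5%.

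The step from a missing sentence to lost error control does not stand. It needs a type of claim that the plan never authorises and that contradicts its own two-sided error statement. For the second secondary it also needs a combination of true effects that the shared Procedure Day count makes very unlikely. The remaining case, one cohort significant on the first secondary, is already handled: the sequence stops there. SAP 5.4.2.1 still reports the proportions and confidence intervals by cohort, so the result can be described without being claimed.

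**Conclusion.** No change is needed. This is a gap in wording that an analyst fills correctly from the gates, the single-claim objectives and the error-control statement: a secondary endpoint is established only if both cohorts reach 0.05. Under that rule the false-claim rate is 0.25% to at most 5%, which matches the SAP, and the tests, alpha and sample size stay as they are. Higher figures arise only under a reading that no section supports.

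The error rates rest on independent cohorts and two-sided 0.05 tests, both taken from the documents. The frequencies for a one-cohort result rest on proxy rates and assumed platelet distributions, and the conclusion does not depend on them. The primary endpoint and the rule for a positive study are not affected.

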### 5.3.4 Examination of Subgroups

Subgroup analysis of primary efficacy endpoint will be performed using age group ( $<65$  and  $\geq 65$  years old), sex (male and female), race (white, black, Asian, and other), geographic region, bleeding risk associated with procedure (low, moderate, and high based on Amendment 02 categorization), MELD score ( $<10$ , 10-14, and  $>14$ ), and CTP grade (A, B, and C). Additional subgroup analysis may also be explored, if deemed appropriate.

### 5.3.5 Handling of Missing Data, Drop-outs, and Outliers

Unless stated otherwise, missing values will be considered as non-responders in responder analyses for all efficacy analyses; observed data will be used in other type of efficacy analyses. Details can be found in [Sections 5.4, Efficacy Analyses](#).

All safety analyses will be performed based on the observed data only.

### 5.3.6 Other Considerations

None

## 5.4 EFFICACY ANALYSES

The FAS will be used as the primary population for the efficacy analyses, while the PP will be used as a supportive analysis. All analyses of platelet counts will be based on local laboratory results.

### 5.4.1 Primary Efficacy Analyses

The primary efficacy variable is the proportion of subjects who do not require a platelet transfusion or any rescue procedure for bleeding after randomization and up to 7 days following an elective procedure.

The null hypothesis is that the proportion of subjects not requiring a platelet transfusion or any rescue procedure for bleeding after randomization and up to 7 days following an elective procedure is the same between the avatrombopag and placebo treatment groups. The corresponding alternative hypothesis is that the proportion of subjects not requiring a platelet transfusion or any rescue procedure for bleeding after randomization and up to 7 days following an elective procedure is not the same between avatrombopag and placebo. This hypothesis will be tested separately with each baseline platelet count cohort.

The proportion of subjects not requiring a platelet transfusion or any rescue procedure for bleeding will be tested between the individual avatrombopag treatment group (40 or 60mg) and matching placebo within each baseline platelet count cohort ( $<40 \times 10^9/L$  or from 40 to  $<50 \times 10^9/L$ ), each at a significance level of  $\alpha=0.05$  using the generalized Cochran Mantel Haenszel (CMH) test adjusting for the risk of bleeding associated with the elective procedure (low, moderate, or high based on Amendment 02 categorization).

- For subjects with platelet count  $<40 \times 10^9/L$  at baseline, the treatment comparison will be carried out between the 60 mg avatrombopag treatment group (Group A) versus matching placebo (Group B).
- For subjects with platelet count from 40 to  $<50 \times 10^9/L$  at baseline, the treatment comparison will be carried out between the 40 mg avatrombopag treatment group (Group C) versus matching placebo (Group D).

This study will be considered as positive if statistical significance is achieved for primary efficacy endpoints for both baseline platelet count cohorts.

The 95% CI for the proportion of subjects not requiring a platelet transfusion or any rescue procedure for bleeding will be calculated for each treatment group within each baseline platelet count cohort. In addition, the 95% CI for the difference between avatrombopag and matching placebo will also be provided within each baseline platelet count cohort using normal approximation method.

Since the HCC status is included in the randomization stratification for safety purposes only, not for efficacy consideration, HCC will not be included in the CMH model for the primary efficacy analysis.

Subjects with missing information about the primary efficacy outcome due to early withdrawal or other reasons will be considered as having received a transfusion for the primary analysis.

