Study E5501-G000-202 evaluated the efficacy, safety, and population PK of once-daily oral avatrombopag dosing, in subjects with chronic liver diseases and thrombocytopenia prior to elective surgical or diagnostic procedures. The primary efficacy endpoint was the proportion of responders with platelet count increases from baseline of $\geq 20 \times 10^9/L$ and a platelet count of $\geq 50 \times 10^9/L$ once from Day 4 through Day 8. The proportion of responders for all avatrombopag-treated subjects was 48.4% compared with 8.1% in the combined placebo group ($P < 0.0001$). All doses of avatrombopag achieved a significantly higher proportion of responders compared with their respective cohort placebo arms and the highest platelet count responses were observed between Days 10 to 14 after first dose. In addition, avatrombopag appeared well tolerated in this patient population. There was no clear trend regarding the incidences of AEs between placebo and avatrombopag treatment groups, and the commonly reported treatment-emergent adverse events (TEAEs) and serious TEAEs were consistent with the disease state of the patient population. The findings from Study E5501-G000-202 suggest that avatrombopag would be an effective therapy for the treatment of thrombocytopenia in patients with chronic liver disease, prior to an elective procedure.

For more detailed information regarding effects in humans, please refer to the Investigator Brochure.

7.1.2.4 Common Serious Adverse Events Expected to Occur in the Study Population Even in the Absence of Study Drug Exposure

Thrombotic/thromboembolic complications may occur in patients with chronic liver disease. Portal vein thrombosis (PVT) is of particular concern in chronic liver disease patients who are prone this type of thrombosis and is often associated with poor portal vein flow. The presence of thrombocytopenia can increase the potential for bleeding, which results in an elevated morbidity and mortality risk in patients with liver disease. In cirrhotic patients undergoing abdominal surgery, bleeding accounts for up to 60% of all causes of death. Thrombocytopenic patients often require multiple platelet transfusions, which can be associated with complications such as systemic infections, iron overload, and platelet refractoriness.⁴

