#### 4 DETERMINATION OF SAMPLE SIZE

The proposed sample size was based on comparisons of the primary efficacy variable, with the response rate defined as the proportion of subjects who do not require a platelet transfusion or any rescue procedure for bleeding after randomization and up to 7 days following an elective procedure. Based on clinical opinion and the published results of a similar compound in adults with thrombocytopenia associated with liver disease (ELtrombopag EVALuated for its Ability to overcome Thrombocytopenia and Enable procedures [ELEVATE] study [Afdahl, 2012]), the response rate in the placebo group is assumed to be 18%. Within each baseline platelet count cohort, a sample size of 100 randomized subjects, 67 subjects for avatrombopag and 33 subjects for placebo, would have greater than 90% power to detect an absolute difference of 35% between the avatrombopag response rate and the placebo response rate assuming 18% response rate for placebo using Fisher's Exact tests with a 2-sided  $\alpha=0.05$ . The hypothesized treatment group difference was based on platelet count changes found in the Phase 2 study (E5501-G000-202) and dose-response modeling using data from that study and others in the project development. Based on the baseline data in the Phase 2 study and assuming these were projected to be similar for this study, it was anticipated that this study would enroll roughly half of the total number of subjects in each of the 2 baseline platelet count cohorts to make the total sample size of 200 randomized subjects, 133 subjects for avatrombopag and 67 subjects for placebo.

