##### 5.4.2.1 Proportion of subjects achieved platelet counts of $\geq 50 \times 10^9/L$ on the Procedure Day

The proportion of subjects who achieve platelet counts of  $\geq 50 \times 10^9/L$  on the Procedure Day will be analyzed first.

The proportion of subjects with platelet counts of  $\geq 50 \times 10^9/L$  on the Procedure Day will be tested between the individual avatrombopag treatment group (40 or 60mg) and matching placebo separately within each baseline platelet count cohort ( $< 40 \times 10^9/L$  or from 40 to  $< 50 \times 10^9/L$ ), each at a significance level of  $\alpha=0.05$  using the generalized CMH test adjusting for the risk of bleeding associated with the elective procedure (low, moderate, or high based on Amendment 02 categorization).

The 95% CI for the proportion of subjects with platelet counts of  $\geq 50 \times 10^9/L$  on the Procedure Day will be calculated for each treatment group within each baseline platelet count cohort. In addition, the 95% CI for the difference between avatrombopag and placebo will also be provided within each baseline platelet count cohort using normal approximation method.

Subjects with missing platelet count on Procedure Day will be considered as not achieving the platelet count of  $\geq 50 \times 10^9/L$  for this analysis.

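### The normal-approximation CI for the primary and first secondary differences can exclude zero when the deciding CMH test is not significant; a stratified Miettinen-Nurminen interval would agree with the test

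*SAP*

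**What the plan says.** SAP 5.4.1 tests the primary endpoint separately in each platelet cohort, "using the generalized Cochran Mantel Haenszel (CMH) test adjusting for the risk of bleeding associated with the elective procedure". For the treatment effect it adds that the "95% CI for the difference between avatrombopag and matching placebo will also be provided within each baseline platelet count cohort using normal approximation method".

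SAP 5.4.2.1 pairs test and interval in the same way for the first secondary endpoint. The test is run "using the generalized CMH test adjusting for the risk of bleeding associated with the elective procedure", and the "95% CI for the difference between avatrombopag and placebo will also be provided within each baseline platelet count cohort using normal approximation method".

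Neither section says whether the interval is stratified, how strata would be weighted, or which variance is used. Protocol 9.7.1.6 promises a 95% CI for the primary difference and names no method.

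The interval has no role in the decision. SAP 5.3.3 states: "The primary efficacy endpoint is considered positive only if the tests are statistically significant for both baseline platelet count cohorts".

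For the second secondary endpoint (SAP 5.4.2.2) the SAP does match interval to test: a Wilcoxon rank sum test, with the difference estimated "using Hodges-Lehmann estimation along with associated asymptotic (Moses) 95% CIs".

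**The concern.** The CMH uses the variance that holds when the two arms share one response rate. A normal-approximation interval, in its usual form, uses each arm's own observed rate. With 2:1 allocation and the lower rate in the smaller arm, the second variance tends to be smaller, so the interval is too short near the significance boundary. Both cohorts must succeed, so one borderline cohort can settle the trial. That is where the report could show a failed test next to an interval that excludes zero, with nothing pre-specified to explain the conflict. The interval is also the published measure of effect and should cover at about its nominal 95%.

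**Working it through.** **Inputs.** SAP section 4 says that "67 subjects for avatrombopag and 33 subjects for placebo, would have greater than 90% power to detect an absolute difference of 35" percentage points, from an 18% placebo rate, by two-sided Fisher's exact test at 0.05. So n1=67, n0=33, N=100 per cohort, and the planned rates are 53% and 18%. Missing primary outcomes count as transfused, so denominators stay at 67 and 33. The interval is taken as an unpooled Wald interval.

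**The plan's own figure.** Enumerating all outcomes at 53% versus 18%, Fisher's exact test has 92.6% power per cohort. The stated power above 90% is reproduced.

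**One borderline table, one stratum: 25/67 versus 6/33.**

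- Difference: 0.3731 − 0.1818 = 0.1913.
- Unpooled SE = √[p1(1−p1)/n1 + p0(1−p0)/n0] = √[0.2339/67 + 0.1488/33] = √0.00800 = 0.0894.
- Normal-approximation CI: 0.1913 ± 1.96 × 0.0894 = 0.016 to 0.367. It excludes zero.
- Null SE, with pooled p = 31/100: √[0.31 × 0.69 × (1/67 + 1/33) × 100/99] = √0.00977 = 0.0989.
- CMH: z = 0.1913/0.0989 = 1.935, p = 0.053. Not significant.
- Miettinen-Nurminen score CI: −0.003 to 0.352. It includes zero and agrees with the test.

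The gap comes from the placebo term. The unpooled form gives 0.1488/33 = 0.0045; the null form gives 0.2139/33 = 0.0065 before the 100/99 factor. At 67 versus 33, 22 tables have a normal-approximation CI above zero and a non-significant one-stratum CMH.

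**All outcomes, one stratum, exact.**

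| True rates | CI coverage | CI and CMH disagree |
|---|---|---|
| 53% v 18% (planned) | 94.0% | 1.5% |
| 38% v 18% (assumed borderline) | – | 8.0% |
| 18% v 18% (no effect) | 94.0% | 3.1% |

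With no effect, the CI excludes zero in 6.0% of trials and the CMH rejects in 4.8%. Miettinen-Nurminen coverage at 53/18 is 94.9%. At 53/18 and 38/18 nearly all disagreement is a CI excluding zero with a non-significant CMH.

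**Three risk strata, simulated.** The risk mix is assumed: 60/20/20 or 60/30/10, with an odds ratio of 1 or 0.6 per risk level. Disagreement with the three-stratum CMH:

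| Interval | 53/18 | 38/18 | 18/18 |
|---|---|---|---|
| Crude normal approximation | 1.0–1.3% | 6.1–7.3% | 3.0–3.1% |
| Stratified normal approximation (Mantel-Haenszel, Sato variance) | 1.1–1.3% | 6.8–7.2% | 3.0–3.1% |
| Unstratified Miettinen-Nurminen | 0.4–0.7% | 1.1–1.9% | 0.3–0.5% |
| Stratified Miettinen-Nurminen, Mantel-Haenszel weights | 0% | 0% | 0% |

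Stratifying a normal-approximation interval therefore gains nothing; the variance is the main cause. Simulations with fixed stratum sizes and equal rates across strata gave the same picture for the crude interval (about 1.5% at 53/18 and 7.7% at 38/18).

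The zero in the last row is an identity. With Mantel-Haenszel weights and the N/(N−1) factor in each stratum's variance, the score statistic at zero difference is the CMH statistic. Its coverage was 94.8–95.3%.

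**The same example in three strata.** Assume stratum sizes 40/20, 17/8 and 10/5, with responders 16, 6, 3 versus 4, 1, 1 (again 25/67 versus 6/33). CMH p = 0.054; stratified Miettinen-Nurminen CI −0.4 to 35.4 points. With one more avatrombopag responder (16, 6, 4), CMH p = 0.040 and the CI is 1.0 to 36.9. The two agree both times.

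**First secondary endpoint.** The documents give no expected rates. Protocol 7.1.2.3 reports a similar but not identical Phase 2 endpoint: "The proportion of responders for all avatrombopag-treated subjects was 48.4% compared with 8.1% in the combined placebo group". At those rates coverage is 94.1% and disagreement 0.2%. If both arms were at 8.1%, coverage would be 92.2% and the CI would exclude zero in 7.8% of trials, against 3.9% for the one-stratum CMH.

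**The case against.** The strongest reply is that little depends on this. The CI decides nothing, and at the planned effect the disagreement is 1.5% per cohort with coverage only one point below nominal. At 53/18 and 38/18 essentially all the discordant tables have a CMH p between 0.05 and 0.08, which a careful reader would call borderline anyway. The 8.0% needs an assumed 20-point effect and is close to the worst case (8.6% at 33% versus 18%). All of this stands, and it is why the point is minor. The 8.1% versus 8.1% case is also remote, because the first secondary endpoint is formally tested only after the primary succeeds in both cohorts.

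A crude interval has one real merit: it matches the arm proportions shown in the table. In the simulated settings the weighted difference departs from the crude one by 0.2–0.4 points on average (95th percentile 0.6–1.2). Those settings assumed blocks of 3, and the protocol gives no block size. Analysis strata follow the Amendment 02 risk categories, so subjects randomised earlier may sit in a different stratum and the gap could be somewhat larger. That is a reason to show both, not to keep the present interval.

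Exact agreement needs the right variant of the score interval. Without the N/(N−1) factor, about 0.1–1.2% of trials still have a CI excluding zero with a non-significant CMH; with inverse-variance weights about 0.6–6% disagree in one direction or the other. The SAP text should therefore name both the weights and the factor.

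SAP 5.4.3.5 uses the same approximation for WHO bleeding score ≥2. No test is paired with it there, so this conflict cannot arise.

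**Conclusion.** The concern holds as a cheap improvement to reporting. The planned interval is slightly too short and can contradict the deciding test: 1.5% of trials per cohort at the design effect, about 6–8% for a borderline 38% versus 18%, and about 3% with no effect. Exact coverage is 94.0% at the planned rates. Success, type I error and power are unaffected.

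This rests on reading the SAP's phrase as an unpooled Wald interval, which is its usual meaning, on 67 versus 33 per cohort, and on the assumed risk mix for the stratified figures. When placebo response is high (from about 17/33) the conflict can reverse, with a significant CMH and a CI that includes zero.

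**What to change.** In SAP 5.4.1 and 5.4.2.1, replace the normal-approximation phrase for the difference CI with:

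> the Mantel-Haenszel weighted difference over the same bleeding-risk strata (Amendment 02 categorization) as the CMH test, with a stratified Miettinen-Nurminen (score) 95% CI, using weights n1·n0/N and the N/(N−1) variance factor in each stratum.

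Show the crude arm proportions alongside. If the sponsor prefers a difference that equals those displayed proportions, an unstratified Miettinen-Nurminen interval removes most of the disagreement, though not all. Leave the CMH tests and SAP 5.4.2.2 as they are.

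The cost is two SAP phrases and a short program step, made before unblinding, with no new data. Protocol 9.7.1.6 fixes no CI method and Protocol 9.7.5 provides for SAP revision, so no protocol amendment is needed. The downside is that the weighted difference may not exactly equal the difference of the displayed proportions.
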